## Grade and Relatedness of Adverse Events:

Adverse Events are graded for severity and scored for relatedness to the protocol, according to a published scale. Several standardized AE Reporting scales are available. (See Help for links to these scales.)

\* Please indicate the scale you intend to use:

- ☐ CTC v2.0 ( <http://ctep.info.nih.gov/reporting/ctc.html> )
- ☐ CTCAE v3.0 ( [http://ctep.info.nih.gov/protocolDevelopment/electronic\\_applications/docs/ctcae3.pdf](http://ctep.info.nih.gov/protocolDevelopment/electronic_applications/docs/ctcae3.pdf))
- ☐ CTCAE v4.0 ( [http://evs.nci.nih.gov/ftp1/CTCAE/CTCAE\\_4.03\\_2010-06-14\\_QuickReference\\_8.5x11.pdf](http://evs.nci.nih.gov/ftp1/CTCAE/CTCAE_4.03_2010-06-14_QuickReference_8.5x11.pdf))
- ☒ CTCAE v5.0  
([https://ctep.cancer.gov/protocoldevelopment/electronic\\_applications/docs/CTCAE\\_v5\\_Quick\\_Reference\\_8.5x11.pdf](https://ctep.cancer.gov/protocoldevelopment/electronic_applications/docs/CTCAE_v5_Quick_Reference_8.5x11.pdf))
- ☐ AIDS Clinical Trials Group (<http://aactg.s-3.com/>)
- ☐ Other

### 24.7 Reporting Adverse Events

**All AEs will be reported to the IRB at least annually.**

#### Reporting Serious AEs

- ☒ Serious Adverse Events, (SAEs) will be reported to the IRB according to policy, within two working days of identification of the SAE.

Select all that apply:

- ☐ SAEs will be reported to the Sponsor and or ESCROW

SAEs will be reported to the sponsor within how many days of the event?

- ☐ SAEs will be reported directly to the FDA, per 21 CFR 312

SAEs must be reported directly to the FDA within 7 days of the event by the investigator/sponsor.

☐ SAEs will be reported to another entity

Describe:

#### **Reporting Unanticipated AEs:**

Select all that apply:

☒ UAEs will be reported to the IRB

UAEs that are related and greater than moderate severity must be reported to the IRB according to policy, within two working days of identification of the UAE.

☐ UAEs will be reported to the Sponsor

UAE will be reported to the sponsor within how many days of the event?

☐ UAEs will be reported to the FDA, per 21 CFR 312

UAEs will be reported to the FDA, per 21 CFR 312, within 15 days.

☐ UAEs will be reported to another entity

Describe:

### **24.8 Reporting Unanticipated Problems**

☒ Unanticipated problems involving risks to participants or others will be reported to the IRB and the CRSO within five working days.

### **24.9 CLIA/CLEP**

**Only laboratory and research tests that are CLIA/CLEP certified or waived may be used to determine eligibility, shared with research volunteers, and used in clinical decision making.**

Select if applicable:

☐ This study includes tests that are not CLIA/CLEP certified; the results of such tests will not be used in clinical decision making, or to determine eligibility, or shared with participants or their health care providers.

### **24.10 Tissue Repository**

**Human Tissue and Data Repositories collect, store, and distribute human tissue materials and or data for research purposes. Repository activities involve three components: (i) the collectors of tissue samples\data; (ii) the repository storage and data management center; and (iii) the recipient investigators.**

\* Select one:

- ☒ I DO NOT intend to collect, store, and distribute human tissue materials for research purposes
- ☐ I DO intend to collect, store, and distribute human tissue materials for research purposes, therefore this protocol entails the Operation of a Tissue Repository. The IRB requires that the protocol specify the conditions under which data and specimens may be accepted and shared, and ensuring adequate provisions to protect the privacy of participants and maintain the confidentiality of data.

If you do intend to collect, store, and distribute human tissue materials, you will be asked to upload the following documents later on in the submission:

- A Sample collection protocol (for tissue collector collaborators to follow) and informed consent document for distribution to tissue collectors and their local IRBs.
- A Certificate of Confidentiality (to protect confidentiality of repository specimens and data).
- A Recipients Agreement describing the commitment of the recipient to preserve the anonymity of the samples shared.

## 25.0

### Toxicity Management and Stopping Rules

#### 25.1 \* Describe any drug toxicity or other conditions under which the participation of a participant or the conduct of the study would be stopped in order to maximize safety (e.g., toxicity management and stopping rules):

If a participant develops an allergic reaction to diazepam, reaction will be immediately treated accordingly with severity of symptoms ie if patients develops rash he/she will be treated with Benadryl, if on the other hand patient develops anaphylactic shock, patient will be given epinephrine intramuscular injection and stabilized (placed on a stretcher, the emergency medical response system will be activated, other support therapies such as intravenous hydration and oxygen will be provided as needed, vital signs monitored), and the participant will be transferred to the Weill Cornell Emergency Room for further management. The participant's Primary Care Provider will be notified of any change in the participant's medical condition.

If patients develop allergic reaction to amoxicillin, he/she will also be instructed to cease the medication and call us and his/her PCP. He/she will be excluded from the study and advised to follow up with PMD.

If the participant cannot tolerate the fleet enema, he/she will be excluded. In addition, if he/she cannot tolerate the flexible sigmoidoscopy due to pain, he/she will be excluded.

If the participant has abnormal vital signs ie T>100.4, BP<80/50 or BP>140/90, HR<50 or HR>100 during any of the study visits, he/she will be excluded.

If a participant starts taking other antimicrobial medications he/she will be excluded from the study.

If a participant starts taking a medication that has adverse interactions with amoxicillin, he/she will be excluded from the study.

If a participant develops renal or liver disease that requires adjustment of amoxicillin dose, he/she will be excluded from the study.

#### \* Indicate withdrawal criteria and procedures below:

If a participant cannot tolerate antibiotics he/she will receive partial compensation. If a participant cannot undergo flexible sigmoidoscopy due to discomfort he/she will receive

partial compensation. These participants will be excluded from the study. If a participant needs to take any other anti-microbial and/ or has an enteric infection while being in the study, he/she will be excluded. The PI will also determine whether other medical conditions developed during the study qualify as withdrawal criteria.

## 26.0 Compensation/Costs

### 26.1 \*Will any compensation be offered to participants in return for their participation, e.g., direct payment, medical care, tests, etc.?

- ☐ No  
☒ Yes (Please describe)

Please Describe

Participants will receive \$1100 for their participation and completion of the study.

- \$300 for each completed sigmoidoscopy procedure
- \$100 for completing a 7-day course of antibiotics

Participants will receive an additional \$100 for completion of all study visit requirements. If a participant only completes a portion of the study, they will receive partial compensation.

### 26.2 \* Will there be any costs to participants associated with their participation in research?

- ☐ Yes ☒ No

## 28.0 Appendices

### 28.1 Enter your appendices below:

None

## 29.0 Funding

### 29.1 \* Do you have sufficient financial resources to support your study?

☒ Yes ☐ No

### 29.2 If this study is/was pilot funded, please specify dates of funding:

From date:

06/01/2022

To date:

12/31/2023

### 29.3 Source of investigational agents:

- ☒ N/A (no investigational agents)  
☐ Provided by a pharmaceutical sponsor/partner with funding as described below  
☐ Provided by a pharmaceutical sponsor/partner without additional funding  
☐ Provided by investigator, participants, or other

### 29.4 Specify funding by Rockefeller University, industry sponsor and/or grant:

Search for a sponsor

	Sponsor	Funding
Rockefeller University	CTSA Pilot Grant	
Industry		
Grant		

**Pilot  
Award**

**29.5 List grants in which this study is named:**

	PHS or Non- PHS	Program	Grant Number	Grant Name	From Date	To Date
No results found						

**30.0 Clinical Services**

**30.1 \*What is the general health status of your study group(s)?**

- ☒ Well/Minimally Ill  
☐ Moderately Ill  
☐ Severely Ill  
☐ Other  
☐ Not Applicable

If other than Well/Minimally Ill, please describe:

**30.2 \* Does your study group have special care needs?**

☐ Yes ☒ No

**30.3 \* Does your study have special equipment needs?**

☒ Yes ☐ No

If Yes, please describe:

Sigmoidoscopy equipment.

**30.4 \* Will you require storage space on the clinical units for supplies to conduct this study?**

☐ Yes ☒ No

**30.5 \* Is special training of hospital staff required?**

☐ Yes ☒ No

**31.0 Pharmacy Services**

**31.1 \* Does the study require Pharmacy Services?**

☒ Yes ☐ No

If Yes, please proceed to next section.

### 31.2 Types of pharmacy services required:

- ☒ Dispensing
- ☐ Randomization
- ☐ Compounding
- ☐ Other

### 31.3 Dispensing:

- ☐ Sponsor supplied drugs
- ☒ Pharmacy supplied drugs
- ☐ Other

### 31.4 Type of medication(s):

- ☐ Injectable
- ☐ Ophthalmic
- ☐ Inhalational
- ☐ Topical
- ☐ Suppository
- ☒ Other

If Other, please specify:

Oral

## 32.0 Bionutrition

### 32.1 \* Will study require patient meals?

☒ Yes ☐ No

If Yes, please specify:

Type of Diet	In/Outpatient	Pack Meal
Standard	 Inpatient  Outpatient	 Pack Meal
Therapeutic	 Inpatient  Outpatient	 Pack Meal
Research Diet	 Inpatient  Outpatient	 Pack Meal
Formula Diet	 Inpatient  Outpatient	 Pack Meal

Nutrient(s) to be controlled (specify):

### 32.2 Will meal times be altered?

☒ Yes ☐ No

If Yes, please explain:

Participants have been asked to refrain from consuming any meals until the procedure is finalized.

### 32.3 Does the protocol require any of the following activities?

- ☐ Food Frequency Questionnaire
- ☐ Bod Pod/ Anthropometric Measurements
- ☐ Diet History/ Food Records
- ☐ Diet/ Nutrition Education

### 32.4 Will food be provided to caregiver, parent or significant other?

☐ Yes ☐ No

### 32.5 For metabolic diets, is diet homogenization required for nutrient analysis by independent lab?

☐ Yes  
☐ No  
☐ N/A

## 33.0 Clinical and Translational Research Facilitation Office

### 33.1 Indicate navigation assistance requested and/or received in the development of the study:

	Requested	Received
Protocol Development		
Protocol Implementation		
Protocol Conduct		
ACCTS/IRB Submission		

### 33.2 Indicate additional education assistance requested and/or received in the development of the study:

	Requested	Received
--	-----------	----------

IND		
IDE		
Team Science Education		
Study Progress Meeting		
Investigator Responsibilities		
Regulatory Binder/Folder		
Source Documentation		
Participant Involvement in Research		

### 34.0 Clinical Research Support Office Resources (CRSO)

#### 34.1 Indicate regulatory input assistance requested and/or received in the development of the study:

Regulatory Support/Design	Requested	Received
General, Vulnerable Populations, Minors, Group Harms		
IND/IDE advice, assistance, and referral		
Informed Consent/Assent		
Data Safety Monitoring Plan		
Clinical Trial Registration		

Plan For Return of Research Results		
Audit/Monitoring Service, Referrals, SOPs		

**34.2 Indicate recruitment assistance requested and/or received in the development of the study:**

Recruitment of Participants	Requested	Received
Recruitment Planning and/or written Plan		
Advertising Strategy, Content, Placement		
Repository/Research Match Queries		
Call Center/Prescreening/Scheduling		
Cost Sharing for Advertising		

**34.3 Indicate community engaging assistance requested and/or received in the development of the study:**

Community Engagement	Requested	Received
PHI Statement/Engaging Stakeholders Section		
CEnR Navigation – fostering pt/community partnership		
Outreach to community/partner/advocacy group/CE Studio		

**34.4 Indicate other assistance requested and/or received in the development of the study:**

Other	Requested	Received
-------	-----------	----------

Survey design, fielding, validation		
Data transfer and security planning		

### 35.0

## BERD: Biostatistics, Epidemiology and Research Design Resource

### 35.1 Indicate the Biostatistical assistance requested and/or received in the development of this study:

	Requested	Received
Development of experimental design		
Power analysis/Sample size determination (# of subjects)		
Navigation (Did Statistician participate in a navigation meeting)		
Randomization schedule		
Data analysis		
Development of new statistical techniques for data analysis (Statistical research)		
Protocol implementation		
Other		

### 35.2 If you are/will be using data analysis specify:

- ☒ Exploratory
- ☐ Descriptive
- ☐ Hypothesis testing
- ☐ Statistical modeling
- ☐ Other

**35.3 If you are/will be assisted with protocol implementation, specify:**

- ☐ Publication
- ☐ Conference
- ☐ Other (type of dissemination)
- ☐ Grant(s)

## 36.0 Biomedical Informatics Resources

**36.1 Indicate Bioinformatics assistance requested and/or received in the development of this study:**

	Requested	Received
Microarray analysis		
Pathway analysis		
RNA-seq analysis		
Bioinformatics training and consultation		
Bioinformatics experimental design		
HPC computing		
Other		

**36.2 If you are/will be using pathway analysis software, specify:**

- ☐ Ingenuity IPA
- ☐ David
- ☐ GSEA
- ☐ Other

**36.3 If you are/will be using RNAseq analysis software, specify:**

- ☐ Tophat
- ☐ Cufflinks
- ☐ Cuffdiff
- ☐ CummmRbund
- ☐ STAR
- ☐ featureCounts
- ☐ DESeq2
- ☐ VOOM
- ☐ RNA-SeQC

If other, specify:

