## 12.8 \* Secondary Outcome(s)

Indicate which **additional variable(s)** will be assessed to judge the secondary outcome(s). Give measurement units, if applicable.

- a. Gene expression profiles in the mucosa and submucosa compartments in humans before and after course of antibiotics.
- b. Gut microbiota changes in humans after course of antibiotics.
- c. Gut metabolites changes in humans after course of antibiotics.

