#### Lab Procedures

Sample processing and analysis.

A total of 20 biopsies will be obtained per participant: 4 will be used for tissue immunostaining and remaining 16 will be used for single nuclei sequencing. Tissue obtained from each region will be separated: four biopsies will be pinned and fixed in 4% paraformaldehyde overnight, followed by washing, permeabilization, and staining of the tissue with the neuronal antibody ANNA-1 and anti-Sox10 which is a glia antibody. We will image the samples with a confocal microscope, and we will count the neurons and glia. Sixteen biopsies will be snap frozen in liquid nitrogen and stored in a -80C freezer. Once several samples have been collected, we will defrost them and further process them into single nuclei suspensions that will be utilized to generate sequencing libraries with the 10X Chromium platform. We will sequence the nuclear RNA to determine the expression of multiple genes in the human intestine. Of note, we do not know what the nuclei yield will be for the pooled 16 biopsies obtained per participant, our target nuclei count will be about 20,000 in total. We will enrich the desired populations by staining the nuclei with anti-NeuN and anti-Sox10 to sort the neurons and glia populations respectively. We do not know what will be the proportions of the different cell types for this particular protocol, however, based on other studies we expect small proportion of glia and neurons thus making it necessary to pool samples from several participants. We will not sequence the human DNA. We will isolate bacterial DNA from the stool and perform 16S ribosomal RNA sequencing for which we have an optimized protocol in our lab. Moreover, we will identify and measure stool metabolites via Liquid Chromatography- Mass Spectrometry at RU Proteomics Core.

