**12.10 \* Data Analysis**

Describe method(s) of data analysis.

In this pilot study, with 10 participants, we will assess the change in the outcomes between baseline and follow up using a paired sample t-test. While exploratory, we will be able to detect a 1.3 standard deviation change in outcomes pre versus post, with greater than 80% power, holding Type I Error to 5%.

**12.11 \* Explain the rationale for the choice of statistical measures and the number of participants proposed for the study, including the power calculations when applicable.**

Assuming we can enroll 10 patients, we will have over 80% power to detect a 1.3 standard deviation difference in continuous outcome measures and a 38% absolute difference in proportions (assume base rate of 50%). This pilot study will also provide observed effect size for use in the design of future analysis.

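### The only stated analysis, a paired t-test, is on its literal reading also the gene-expression analysis, and would detect substantially fewer true changes than a paired variance-moderated model at the same false discovery rate

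*Combined protocol and SAP*

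**What the plan says.** Section 12.8 lists as secondary outcome (a): "Gene expression profiles in the mucosa and submucosa compartments in humans before and after course of antibiotics". Under Lab Procedures in section 12.9, expression is measured by single-nuclei RNA sequencing.

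The Data Analysis section (12.10) is one short paragraph. "In this pilot study, with 10 participants", it says, "we will assess the change in the outcomes between baseline and follow up using a paired sample t-test". It calls the work exploratory and claims to be able to "detect a 1.3 standard deviation change in outcomes pre versus post, with greater than 80% power" at a 5% type I error. It states no gene-level model, normalisation, multiplicity control or unit of analysis for the sequencing data, and nor does any other section.

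Two statements under Lab Procedures bear on precision and on the unit of analysis. On yield: "we do not know what the nuclei yield will be for the pooled 16 biopsies obtained per participant". On scarcity of neurons and glia, which the protocol describes as "thus making it necessary to pool samples from several participants".

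Item 36.3, "If you are/will be using RNAseq analysis software, specify", lists nine tools, DESeq2 and VOOM among them. None is ticked and the free-text line is empty.

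**The concern.** Gene expression is one of the outcomes, and 12.10 assigns a single method to the outcomes. An analyst who follows the text would run a paired t-test gene by gene. With 10 pairs that test has two weaknesses for this kind of data.

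- It estimates each gene's variance from 9 degrees of freedom and borrows nothing from the other genes.
- It gives a profile built from a handful of neuron or glia nuclei the same weight as one built from many, although the protocol says that yield is unknown and expects these cells to be scarce.

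The study aims to identify neuron and glia subtypes that are susceptible to antibiotics. If the test is inefficient, an absence of detected change in a cell type may reflect the test rather than the biology. Section 12.9 records that enrolment closed on May 24, 2024, so the sample size can no longer be raised. The choice of model can still be changed.

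**Working it through.** **1. The plan's own figure.** Inputs from 12.10: n = 10, change d = 1.3 SD (read as SD of the paired differences), type I error 5% (two-sided assumed; not stated). For a paired t-test, df = 10 − 1 = 9 and the noncentrality is d√n = 1.3 × 3.162 = 4.11. Power is 95.4%. The claim of more than 80% is therefore reproduced as a lower bound. The change detectable with 80% power is 1.00 SD.

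**2. Why that figure does not carry over to gene expression.** It describes one test at an unadjusted 5%. At that level the choice of statistic hardly matters: 95.4% for the ordinary test, 96.7–97.4% for a moderated one. But a 5% level per gene cannot serve for a screen. With 20,000 genes (assumed) and no true change, 20,000 × 0.05 = 1,000 genes would be declared changed. Some control is needed, and I assume Benjamini-Hochberg at 5%.

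**3. The two statistics compared.**
- Ordinary: t = mean difference / (s/√10), 9 df.
- Moderated: replace s² by (d₀s₀² + 9s²)/(d₀ + 9), with 9 + d₀ df. Here s₀² is the typical variance across genes and d₀ measures how similar the gene variances are. I take d₀ = 4 and 10 (13 and 19 df).

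If a share π of genes truly changes, the p-value cut-off a solves a = 0.05 × [(1 − π)a + π × power(a)]. At 1.3 SD:
- π = 10%, ordinary: a ≈ 0.0029, power about 55%. Check: 0.05 × (0.9 × 0.0029 + 0.1 × 0.55) = 0.0029.
- π = 10%, moderated (13 df): a ≈ 0.0037, power about 70%. Check: 0.05 × (0.9 × 0.0037 + 0.1 × 0.70) = 0.0037.
- π = 2%, ordinary: a ≈ 0.00012, power about 11%. Check: 0.05 × (0.98 × 0.00012 + 0.02 × 0.11) = 0.00012.

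| Share changed, 1.3 SD | Ordinary (9 df) | Moderated (13 df) |
|---|---|---|
| 1% | 2% | 18% |
| 5% | 34% | 55% |
| 10% | 55% | 70% |
| 20% | 73% | 81% |

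**4. Simulation.** 10 pairs, 2,000 or 8,000 genes, d₀ = 4 or 10, Benjamini-Hochberg 5%:

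| Change | Share changed | Ordinary | Moderated |
|---|---|---|---|
| 1.3 SD | 10% | 55–56% | 70–79% |
| 1.3 SD | 2% | 10–18% | 33–49% |
| 1.0 SD | 10% | 12–13% | 26–38% |

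The realised false discovery rate is about 5% for both tests. Among 2,000 genes with 10% changed, 200 × 0.55 = 110 would be found, against 200 × 0.70 = 140 to 200 × 0.79 = 158.

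**5. Sensitivity.**
- *Variances that do not follow the moderated test's model:* about 56% versus 71–78% (10% changed) and 10–14% versus 35–48% (2% changed).
- *Negative-binomial counts* (10,000 genes, 10% changed), t on the log scale versus moderated t: 64% versus 84% (dispersion 0.1, 2-fold), 22% versus 37% (dispersion 0.2, 2-fold), 71% versus 88% (dispersion 0.2, log2 change 1.5), and about 0% for both at log2 change 0.5.
- *Stricter control:* Bonferroni over 20,000 genes at 1.3 SD gives 0.6% versus 2.0–4.7%.
- *Fewer units:* with 5 pairs and a change of 1.3 SD between units, the ordinary test finds about 0% and the moderated test 0–17%.

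Neither DESeq2 nor limma-voom was itself run. Any gain from weighting for unequal nuclei yield is not included.

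**The case against.** The strongest reply is that the plan never says that it will test genes one at a time with a t-test. Section 12.10 is a brief paragraph about a pilot. Section 12.1 refers to techniques already in use in the laboratory, and 12.4 says that genomics and bioinformatics core staff will help. This stands in part: the gene-by-gene t-test is the literal consequence of the text, not a recorded decision. But staffing is not a specified method, and the literal and the generous reading call for the same edit.

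A reader might infer from the empty boxes in 36.3 that count-based methods were considered and rejected. The documents do not support that. The item is conditional, belongs to a section on informatics support in which every box is blank, and also leaves an aligner (STAR) and a read counter (featureCounts) unticked.

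It is also fair that 10 pairs and the multiplicity threshold cause much of the loss, and that moderation narrows the gap without closing it. The Bonferroni and small-effect results show this.

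Finally, the main simulation draws variances from the model that the moderated test assumes. The gain persists when that is relaxed and when counts are simulated, so this point does not overturn the result.

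**Conclusion.** The point holds. As written, 12.10 makes a paired t-test the only analysis that could apply to outcome (a), and that test is inefficient for these data. Under the assumptions above it detects about 55% versus 70–79% of changed genes when 10% change, and about 10–18% versus 33–49% when 2% change.

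The 1.3 SD is the protocol's generic figure, not an expression effect. The number of genes, share changed, variance distribution and false discovery rate are assumed. Ten participant-level pairs are an upper limit, because pooling across participants is foreseen.

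A reader might go further and conclude that most real changes would be missed. That is true in some scenarios (2% changed, or a 1.0 SD change) and false in others: at 1.3 SD with 10–20% of genes changed the t-test finds 55–73%, and at 2.0 SD it finds 73–99%. The documents do not show which applies.

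The primary cell-count outcome is unaffected. For a secondary outcome of an exploratory pilot this is a change that should be made, not one that invalidates the study.

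**What to change.** In section 12.10:

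1. Confine the paired t-test to the neuron and glia counts. (Outcomes (b) and (c) need their own statement, which is not assessed here.)
2. For outcome (a), sum nuclear counts to pseudobulk per independent unit, visit and cell type. Analyse them with a paired moderated or count model: limma-voom with precision weights, or DESeq2 with participant and visit in the design, with normalisation for library size.
3. State the false discovery rate and the procedure that controls it, and name the visit contrasts, since biopsies are taken at Visits 2, 4 and 5.
4. State the unit of analysis where samples are pooled across participants. Either keep participant identity separable, or treat each pool as the unit (replacing participant in the design) and pool the same participants at each visit.

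Completing 36.3 to match is optional. The cost is a few lines of text and some analyst time. The model change needs no extra tissue, visits or participants; keeping identities separable may add laboratory work. The text should be fixed before the expression data are examined.
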